3.1.2 Creating a Score Set

Create a new score set based on the “sibel” score set. It will contain pre-labeled sleep events from EnsoSleep. Left-click “proceed” to get to the scoring screen as shown in Figure 7.

Select Scoreset

Choose which scoreset to view. Those marked as Read only may not be modified but can be used to generate a new scoreset.

Scoreset

Open

sibel

Read-only

Create

Based on

sibel

[figure not shown]
Name

Scorer 1

Signals only

CANCEL PROCEED

Figure 6: EnsoSleep Scoreset selection Screen

STU#: STU00214445

Figure 7: EnsoSleep Scoring Screen

3.1.3 Configuring the Scoring Screen

On the top right corner of the scoring screen, click the settings icon to modify the time span. A 5-minute timespan is recommended for optimal view of PAT signal changes.

[figure not shown]

Figure 8: Enso Sleep Settings Screen

Utilize the “R” key on the keyboard to rescale all the signals throughout the scoring process.

STU#: STU00214445

[figure not shown]
[figure not shown]

Figure 9: Before and After pressing the R key

Auto scaling obfuscates any evidence of the changes in signal due to heterogeneity in amplitude attributed to regular chest movements and motion artifacts. In order to rescale the two signals only, EnsoSleep provides features to manually adjust the desired scale for each channel. Below is an example where it might look like a chest movement reduction but is actually a zoomed-out view due to motion artifacts.

STU#: STU00214445

Before

After

[figure not shown]

Figure 10: Signal Zoomed Out Due to Motion Artifact

When you see motion artifacts, manually rescale these two signals. You can rescale for each channel by right-clicking on the signal name on the far left side to get a pop-up screen as shown below. Click + or - to adjust the scale.

STU#: STU00214445

[figure not shown]

Figure 11: Rescale Feature

3.1.4 Adding Sleep Disordered Breathing Events

Drag the cursor on the **PAT signal** to label a sleep-disordered breathing event as **Obstructive Hypopnea**. Do not use other event types as the ANNE Sleep system will not distinguish differences among Obstructive Apnea, Hypopnea, and Central Apnea.

[figure not shown]

Figure 12: Enso Sleep Marked Events Scoring Screen

STU#: STU00214445

3.1.5 Deleting Sleep Disordered Breathing Events

To delete an event, right-click the event and click delete.

[figure not shown]

Figure 13: Deleting Events

STU#: STU00214445

For further instructions on how to use the platform described in this section, please refer to EnsoSleep’s instruction manual.

3.2 Detecting Sleep Disordered Breathing Events with ANNE Sleep System

Respiratory events (Apnea episodes) are caused either by an upper airway obstruction following the collapse of the upper airway wall or central dysfunction in which the brain doesn’t send proper signals to the muscles that control breathing. During the apnea episodes, sympathetic activation causes vasoconstriction and acceleration of the heart rate. This results in attenuation of the PAT signals. PAT amplitude may vary due to reasons other than apnea events such as periodic limb movements or spontaneous arousals. This section described the steps necessary to differentiate the true respiratory event resulting in attenuation of the PAT signal and the ones caused by events not related to it.

[figure not shown]

Figure 14: Typical pattern of PAT Amp attenuation and HR increase

STU#: STU00214445

When scoring for sleep-disordered breathing (SDB) events, the first step is to see if the area that is being analyzed has (1) motion artifact or (2) body position change. If there are any of the two signals, do not continue on to see if it is an SDB event.

Next, look at the **Accel Vertical** and **Accel Horizontal** signal for chest movement reduction. If the amplitude of **both** signals drops by 90% or more for more than 10 seconds, it is categorized as an SDB event. If one or both signals does not look as below, move to analyze the attenuation of the PAT signal. Label the event as an SDB regardless of the limb sensor output.

[figure not shown]

Figure 15: Chest Movement Reduction Example

If there are motion artifacts in between the chest movement reduction, do not grade the signal as SDB. An example of it is shown below. This is usually created as part of changing the body position and should be disregarded.

STU#: STU00214445

[figure not shown]

Figure 16: Motion Artifact example

After analyzing the two accelerometer signals and concluding that there is no chest movement reduction, proceed to analyze attenuation of the PAT signal, heart rate increase, and SpO2 drop. PAT attenuation can be easily identified by seeing the PAT amplitude signal drop. Also, heart rate should increase by at least 3 bpm within 15 seconds, and the SpO2 should drop by at least 3% within 60 seconds. If the conditions above are met, label the event as SDB.

If there is a reduction in PAT amplitude and an increase in heart rate but the SpO2 drop is not present, look at the snoring signal. If the area of interest has no snoring but there is snoring before that point, label the event as SDB.

A flow diagram is shown below to summarize the steps necessary to label SDB events using ANNE Sleep.

STU#: STU00214445

[figure not shown]

Figure 17: Flow for detection Sleep Disordered Breathing

3.3 Examples

The following are example snapshots of various SDB (Sleep Disordered Breathing) events covering the different cases in the flow diagram.

STU#: STU00214445

3.3.1 Example 1

[figure not shown]

Figure 18: Example 1: Snapshot of SDB events

Event 1, 4:

- Chest movement reduction ✗
- PAT Amplitude decrease ✓
- $\geq 3\%$ drop in SpO2 ✓
- Pulse Rate Increase ✓

Conclusion: SDB Event

Event 3, 5, 6:

- Chest movement reduction ✗
- PAT Amplitude decrease ✓
- $\geq 3\%$ drop in SpO2 ✗
- Pulse Rate Increase ✓

Conclusion: Not an SDB Event

Event 2:

- Chest movement reduction ✗
- PAT Amplitude decrease ✓
- $\geq 3\%$ drop in SpO2 ✗
- Pulse Rate Increase ✗

Conclusion: Not an SDB Event

STU#: STU00214445

3.3.2 Example 2

[figure not shown]

Figure 19: Example 2: Snapshot of SDB events

Event 1:

- Chest movement reduction ✗
- PAT Amplitude decrease ✗
- Pulse Rate Increase ✓
- 3% drop in SpO2 ✓

Conclusion: Not an SDB Event

Event 2:

- Chest movement reduction ✗
- PAT Amplitude decrease ✓
- Pulse Rate Increase ✓
- 3% drop in SpO2 ✓

Conclusion: SDB Event

Event 3:

- Chest movement reduction ✗
- PAT Amplitude decrease ✗
- Pulse Rate Increase ✗
- 3% drop in SpO2 ✗

Conclusion: Not an SDB Event

3.3.3 Example 3

STU#: STU00214445

[figure not shown]

Figure 20: Example 3: Snapshot of SDB events

Event 1:

- Chest movement reduction ✗
- 3% drop in SpO2 ✗
- PAT Amplitude decrease ✓
- Pulse Rate Increase ✓
- Snoring reduction for more than 10 seconds ✗

Conclusion: Not an SDB Event

Event 2:

- Chest movement reduction for more than 10 seconds ✗
- PAT Amplitude decrease ✓
- Pulse Rate Increase ✓
- 3% drop in SpO2 ✗
- Snoring reduction for more than 10 seconds ✓

Conclusion: SDB Event

STU#: STU00214445

3.3.4 Example 4

[figure not shown]

Figure 21: Example 4: Snapshot of SDB events

Event 1:

- Chest movement reduction ✗
- $\geq 3\%$ drop in SpO2 ✓
- PAT Amplitude decrease ✓
- Pulse Rate Increase ✓

Conclusion: SDB Event

Event 2:

- Chest movement reduction ✓
- $\geq 3\%$ drop in SpO2 ✓
- PAT Amplitude decrease ✓
- Pulse Rate Increase ✓
-

Conclusion: SDB Event

Event 3:

- Chest movement reduction ✗
- PAT Amplitude decrease ✓
- Pulse Rate Increase ✓
- 3% drop in SpO2 ✓

Conclusion: SDB Event

STU#: STU00214445

3.3.5 Example 5

[figure not shown]

Figure 22: Example 5: Snapshot of SDB events

Event 1:

- Chest movement reduction ✗
- 3% drop in SpO2 ✗
- PAT Amplitude decrease ✓
- Pulse Rate Increase ✓
- Snoring reduction for more than 10 seconds ✗

Conclusion: Not an SDB Event

Event 2:

- Chest movement reduction ✗
- 3% drop in SpO2 ✗
- PAT Amplitude decrease ✓
- Pulse Rate Increase ✓
- Snoring reduction for more than 10 seconds ✗

Conclusion: Not an SDB Event

Event 3:

[figure not shown]
- Body Position Change ✗

Conclusion: Not an SDB Event

STU#: STU00214445

3.3.6 Motional Artifact Example

The following is an example of a snapshot that contains large movements. Any events under or between big motion artifacts should not be labeled as SDB. Continuous motion artifacts often relate to the patient being awake or switching body position. With large motion affecting signal quality, the associating vital signs may be invalid.

0

Figure 23: Snapshot of motion artifacts

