9. SCORING

9.1 ANNE™ Sleep Scoring

The data from ANNE™ will be reviewed and scored for respiratory events by three (3) registered polysomnography technicians (RPSGT) who are blinded to the scoring of the HST, and represent scorers in clinical practice in AASM accredited sleep disorder centers. An average will be taken of the three scores. In order to minimize interscorer variability, the technicians will have >85% concordance. To ensure quality and reproducibility, a board certified sleep medicine physician who is blinded to the experimental condition will review all raw HST data. If AHI determined from ANNE™ Sleep exhibits greater than 15% difference between three RPSGTs, a board-certified sleep medicine physician will provide the final determination of the AHI for ANNE Sleep.

Scoring of ANNE™ Sleep data will follow guidelines established by the American Academy of Sleep Medicine Manual for the Scoring of Sleep and Associated Events (v2.6)⁶. Sleep scoring includes the following variables: total sleep time (TST= the total amount of sleep time scored during the total recording time in minutes). The scoring of respiratory events to evaluate for sleep disordered breathing will also follow AASM scoring rules.

The ANNE™ Sleep will be scored similarly with the system’s onboard sensors as an alternative hypopnea and apnea sensor via PAT. The definition of mild, moderate, or severe obstructive sleep apnea is based on AHI.

- AHI < 5: Normal
- AHI ≥ 5 – <15: Mild
- AHI ≥15 – <30: Moderate
- AHI ≥ 30: Severe

The AHI calculated from ANNE™ Sleep will be considered an estimation of AHI, coined as AHI.

An apnea event is defined as:

STU#: STU00214445

- A drop in peak signal excursion by $\geq 90\%$ of pre-event baseline for ≥ 10 seconds using an oronasal thermal signal, PAP device flow, or an alternative apnea sensor.
- No requirement for a desaturation or an arousal

Hypopnea will be defined by:

- The peak signal excursions drop by $\geq 30\%$ of pre-event baseline using nasal pressure (diagnostic study), PAP device flow (titration study), or an alternative hypopnea sensor (diagnostic study)
- The duration of the $\geq 30\%$ drop in signal excursion is ≥ 10 seconds
- There is a $\geq 4\%$ oxygen desaturation from pre-event baseline and/or the event is associated with an arousal

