The scoring of respiratory events to evaluate for sleep disordered breathing will also follow AASM scoring rules. Apnea-hypopnea index will be used to determine the presence and severity of sleep apnea ($AHI = \text{apneas} + \text{hypopneas} * 60 / \text{TRT}$).

The accuracy (sum of the number of true positives and true negatives divided by the sum of the number of true positives, true negatives, false positives, and false negatives), sensitivity, specificity, positive predictive value, and negative predictive value of the ANNE™ Sleep to detect moderate to severe obstructive sleep apnea will be compared to outputs from WatchPAT ONE. A Bland-Altman plot will be generated with 95% confidence to intervals to assess agreement.

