3.0 Scoring Procedure

3.1 Data Flow Overview

The high-level data flow is shown below (Figure 4). After the patient has received the ANNE Sleep system and successfully finished their sleep night data collection, the data is downloaded from the sensors and automatically uploaded to the ANNE Sleep Hub. In the ANNE Sleep Hub, the data collected from the ANNE sensors are processed and converted into an EDF format file so that it can be consumed by EDF viewers and scoring platforms such as EnsoSleep. After the dataset has been scored, the scored data is transferred back to the ANNE Sleep Hub for sleep report generation. The report generated can then be reviewed by a Healthcare Professional (HCP) to aid in the evaluation of sleep-related breathing disorders.

STU#: STU00214445

[figure not shown]

Figure 4: ANNE Sleep Data Flowchart

pAHI (peripheral arterial tonometry AHI) is calculated by counting the number of sleep-disordered breathing events for the patient divided by the TST (total sleep time). TST is automatically calculated in ANNE Sleep Hub using pulse rate.

$$pAHI = \frac{\text{Total Number of Disordered Breathing Events}}{\text{Total Sleep Time (hrs)}}$$

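### Events in or between motion artifacts are barred from the ANNE count, but no rule removes that time from the AHI denominator, so AHI reads low where barred time stays in the denominator and holds true events

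*Combined protocol and SAP*

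**What the plan says.** **Count of events.** The scoring manual (Detecting Sleep Disordered Breathing Events with ANNE Sleep System) makes motion artifact or body position change the first check: "If there are any of the two signals, do not continue on to see if it is an SDB event". For accelerometer signals it adds: "If there are motion artifacts in between the chest movement reduction, do not grade the signal as SDB". Section 3.3.6 extends the bar to the time around artifacts: "Any events under or between big motion artifacts should not be labeled as SDB". In Example 5 (3.3.5), Event 3 is rejected on body position alone.

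**Denominator.** Protocol section 9.1 prints the index as "AHI = \text{apneas} + \text{hypopneas} * 60 / \text{TRT" (typesetting code included), that is, events over TRT, which I read as total recording time. Manual section 3.1 instead divides by total sleep time in hours and states: "TST is automatically calculated in ANNE Sleep Hub using pulse rate". Protocol 9.1 describes TST as "the total amount of sleep time scored during the total recording time in minutes".

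**What is absent.** No section deducts barred time from TRT or says how the TST algorithm classes artifact time. Manual section 3.1.4 tells scorers to label events with one event type only. No instruction has them mark the stretches they skip.

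**Where the index is used.** Protocol 9.1 sets moderate OSA at 15/h and severe at 30/h. Section 4.1 lists between-night AHI variation and same-night agreement with WatchPAT ONE among the primary outcomes.

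**The concern.** A rate needs the same time base above and below the line. Here the scorer's decision that a stretch cannot be assessed removes its events, but nothing described carries that decision into the hours. Where those hours stay in, the index is events found in scorable time divided by scorable plus unscorable time.

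Two primary outcomes use this index. Agreement depends on which side of 15/h a subject falls. Between-night variation is more directly exposed. Subjects apply the sensors themselves at home (8.1.3), on nights that need not be consecutive (8.1.2), so the barred share may differ from night to night. Averaging three scorers does not remove the problem, because all three follow the same rule.

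**Working it through.** The plan states no artifact share, bias or adjusted cut-off, so there is no figure to reproduce. The check is arithmetic on the stated formulas. The cut-offs of 15 and 30/h come from protocol 9.1; every f, k, a and g below is an assumption.

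**General form.** Let f be the share of the denominator in which events are barred, r the event rate in the rest, and kr the rate in barred time.

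- True AHI = r(1-f) + krf
- Reported AHI = r(1-f)
- Reported/true = (1-f)/(1-f+kf)
- True AHI needed to read 15 = 15(1-f+kf)/(1-f), which is 15/(1-f) when k = 1

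**Equal event rate (k = 1).**

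| f | A true 15/h reads | True AHI needed to read 15 | True AHI needed to read 30 |
|---|---|---|---|
| 5% | 14.25 | 15.8 | 31.6 |
| 10% | 13.5 | 16.7 | 33.3 |
| 20% | 12.0 | 18.8 | 37.5 |

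**Dependence on k, at f = 20%.** The cut-off is 15(0.8+0.2k)/0.8: 15.0 at k = 0, 16.9 at k = 0.5, 18.8 at k = 1 and 22.5 at k = 2. If no true events fall in barred time, the bar loses nothing.

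**Under TST.** Let a be the artifact share of sleep plus artifact time, and g the share of artifact time that TST drops as wake. Then f = a(1-g)/(1-ag). At a = 20% and k = 1:

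- g = 0: f = 0.20, cut-off 18.8
- g = 0.5: f = 0.10/0.90 = 0.111, cut-off 15/0.889 = 16.9
- g = 1: f = 0, cut-off 15.0

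The bias under TST therefore runs from the full TRT-type effect down to zero, depending on a classification that the documents do not describe.

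**Between nights.** A subject with a constant true AHI of 30 reads 30 × 0.95 = 28.5 on a night with f = 5% and 30 × 0.80 = 24.0 on a night with f = 20%. The difference of 4.5/h comes from movement alone (k = 1).

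**Check on the remedy.** Subtracting all marked minutes from TST can over-correct. Assume 8 h recorded, 1 h of it wake with artifact, TST 7 h and 105 events. The AHI is 105/7 = 15.0. Subtracting the marked hour again gives 105/6 = 17.5.

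**The case against.** Refusing to score uninterpretable signal is sound practice, and the manual explains why such time may not matter: "Continuous motion artifacts often relate to the patient being awake or switching body position". Wake should not be in a TST denominator. If the algorithm classes all artifact time as wake, numerator and denominator match and there is no bias. The manual also has scorers rescale the chest-movement channels by hand when they see artifact (3.1.3), so signal near an artifact is not simply abandoned.

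Much of this stands, and it rules out several stronger readings.

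- **A reader might infer that the bias is present whichever denominator is used.** Only the TRT formula keeps the barred time in explicitly. Under TST the manual is silent, and silence does not show that artifact time counts as sleep.
- **A reader might infer that the AHI is always lowered.** That requires true events in the barred time. If that time is event-free wake, any dilution under TRT comes from using recording time instead of sleep time, which is the separate TRT/TST conflict.
- **A reader might infer false results below 15/h relative to WatchPAT ONE.** Protocol 9.2 leaves that device's scoring to its operating manual. Both devices are worn on the same night, and how the comparator treats the same movement is unknown.

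The objection does not clear the plan. The manual says that artifact often, not always, reflects wake, and it names position change as another cause. Events between artifacts are barred too, and nothing says that the intervening time is wake. Section 3.3.6 also warns that vital signs may be invalid during large motion; pulse rate, the stated basis of TST, is among them.

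**Conclusion.** The point holds in conditional form. The bar on events is explicit, and no rule matches it in the denominator. With the formula in protocol 9.1 followed as written, the ANNE AHI is lowered whenever true events fall in barred time. Under the manual's TST the same holds only for artifact time classed as sleep, and the bias is zero if all of it is dropped as wake.

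The size cannot be obtained from the documents. The effective cut-offs of 15.8, 16.7 and 18.8/h are illustrations at assumed shares of 5%, 10% and 20% with an equal event rate in lost time; they are not estimates for this study. The direction is firm under TRT and conditional under TST.

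The clearest consequence is for the between-night outcome, where an unequal barred share would appear as AHI variation without any assumption about the comparator. The net effect on agreement with WatchPAT ONE is undetermined. This should be corrected, but it does not invalidate the design.

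**What to change.** In protocol section 9.1 and in manual section 3.1 and the event-detection section:

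1. Reconcile TRT and TST to one stated denominator.
2. Have scorers mark every stretch skipped for motion or position change, including time between large artifacts.
3. Divide events by scorable time: the chosen denominator minus only those marked minutes still counted in it. Under TST this means only marked minutes classed as sleep, so that artifact wake is not subtracted twice. State how the TST algorithm classes artifact time.
4. Report unscorable minutes per subject and night.
5. Show Night One agreement and between-night variation with and without the correction.

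The cost is a change of wording in the two documents and slightly more scorer time within scoring already planned. The downside is a denominator that differs a little from that of earlier ANNE reports; showing results both ways keeps the comparison available.
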